### **Sensitivity analysis**

None

### **Analysis by subgroups**

None

#### *5.3.3.4 Anthropometric and vital signs*

The following vital signs parameters will be summarized in a table using descriptive statistics by treatment group at each study visit (from baseline to week 28) in the safety set of patients:

- Weight (kg),
- Systolic Blood Pressure (mmHg),
- Diastolic Blood Pressure (mmHg).

The corresponding relative changes from baseline will also be described by treatment group at each study visit.

Additionally, will be presented at each study visit the number (%) of patients presenting a relative change from baseline in weight (Decrease of  $\geq 10\%$ , Decrease from  $\geq 5\%$  to  $< 10\%$ , No change (Change within  $-5\%$  ;  $5\%$ ), Increase from  $\geq 5\%$  to  $< 10\%$ , Increase of  $\geq 10\%$ ). A graph reporting the mean (95% CI) weight by visit and treatment group will be provided.

#### *5.3.3.5 Electrocardiogram (ECG)*

The following parameters will be considered for the analyses of ECG:

- Status over time (based on the conclusion of the central reader):
  - o Normal or Abnormal NCS - Normal or Abnormal NCS
  - o Normal or Abnormal NCS - Abnormal CS
  - o Abnormal CS – Normal or Abnormal NCS
  - o Abnormal CS - Abnormal CS
- QT duration corrected according to Fridericia formula (QTcF) (ms)
- QTcF > 450 ms (Yes, No)
- QTcF > 480 ms (Yes, No)
- QTcF > 500 ms (Yes, No)
- Absolute change from baseline in QTcF (ms)
- Absolute change from baseline  $\geq 60$  ms (Yes, No)
- Absolute change from baseline  $\geq 30$  ms (Yes, No)
- HR (beats/min)
- HR in categories ( $<40$  beats/min,  $\geq 40$  and  $\leq 120$  beats/min,  $>120$  beats/min)
- Relative change in HR from baseline ( $\leq 25\%$ ,  $>25\%$ )

Each parameter will be described at each study visit using descriptive statistics by treatment group overall and by gender in the safety set of patients.

Then, for QTcF and HR, will be provided a graph reporting the mean (+/- 95% CI) of the parameter by visit and treatment group.

A listing of abnormal CS interpretation at Baseline and/or over time will be provided.

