### **6.3 Safety Variables**

All safety variables will be primary ones. Safety evaluations will be completed as given in section 9.7 and as indicated below.

The Investigator will rate all safety variables as to clinical relevance or not. In case of a clinically relevant abnormality, the safety evaluation will be repeated. If the abnormality is confirmed and clinically relevant, it will be recorded as an AE term in the eCRF. The abnormality will be followed up until the value has returned to normal or an adequate explanation is found.

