### - **Vital signs and ECG**

Descriptive statistics by time point will be computed on actual values and changes from baseline for vital signs and ECG data. The baseline value is defined as the last measure before study product intake. ECG parameters collected are heart rate, PR interval, QRS interval, QT, QTcB (Bazett) intervals. Descriptive statistics (means, standard deviations, and ranges) and changes from baseline

values for all visits will be provided. The summaries will include patients who have at least one measurement performed after the first study product intake. Results and changes from baseline of the following vital sign parameters will be summarized by mean, standard deviation, median, minimum and maximum at each time point and the final on-treatment visit:

- Heart rate: supine,
- Systolic blood pressure: supine,
- Diastolic blood pressure: supine,
- Weight.

Shift tables and other tabular and graphical methods (plots of mean over time) may be used to present the results for parameters of interest.

Confirmatory–inferential analysis may be done for parameters of interest. Listings will be provided with flags indicating clinically significant out-of-range values, clinically non-significant out-of-range values.

Any ECG modification or change in vital sign compared to screening, considered as clinically significant by the Investigator, will be reported as an AE.

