#### 4.5.6.4 *Electrocardiogram data*

In case of retest for a given parameter:

- Before first treatment intake, the last non-missing value will be selected
- After first treatment intake the first non-missing value during a visit will be selected

Available QTcF will be classified in 3 distinct categories:

- $> 450$  or  $\leq 450$  ms
- $> 480$  or  $\leq 480$  ms
- $> 500$  or  $\leq 500$  ms.

QTcF prolongation (Absolute change in QTcF from baseline) will be classified in 2 distinct categories:

- $\geq 60$  ms and  $< 60$  ms
- $\geq 30$  ms and  $< 30$  ms.

Available HR (Heart Rate) will be classified as:

- $< 40$  beats/min,  $\geq 40$  and  $\leq 120$  beats/min,  $>120$  beats/min

Relative change in HR from baseline will be classified as:

- $\leq 25\%$  and  $>25\%$

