#### 5.1.9 *Anthropometric and vital signs*

- Weight (kg),
- Height (cm),
- BMI ( $\text{kg}/\text{m}^2$ ),
- BMI in class (Underweight, Normal, Overweight, Obese class I (moderate), Obese class II (severe), Obese class III (morbid))
- BMI in class (Non-obese, Obese)
- Waist circumference (cm) (overall and by sex)
- Systolic Blood Pressure (mmHg),
- Diastolic Blood Pressure (mmHg),
- Heart rate (bpm).

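### The SAP omits, without declaring it, the PR, QRS and post-baseline vital-sign heart-rate summaries that the protocol requires, and its heart-rate change class cannot register a fall

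*SAP*

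**What the plan says.** **Protocol.** Section 9.7.3 (Vital signs and ECG) sets the rule: "Descriptive statistics by time point will be computed on actual values and changes from baseline for vital signs and ECG data". It then names the measures. For ECG: "ECG parameters collected are heart rate, PR interval, QRS interval, QT, QTcB (Bazett) intervals". For vital signs the first item is "Heart rate: supine", followed by supine systolic and diastolic pressure and weight. Section 6.3 gives these data their standing: "All safety variables will be primary ones". ECGs are scheduled at V-1, V1 and V3 only (5.2.5). Vital signs are taken at screening and at every visit from V0 to V4 (6.3.3).

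**SAP.** Section 5.3.3.4 begins "The following vital signs parameters will be summarized in a table using descriptive statistics by treatment group at each study visit", and its list is weight, systolic pressure and diastolic pressure. Vital-sign heart rate appears only in the baseline description (5.1.9). Section 5.3.3.5 begins "The following parameters will be considered for the analyses of ECG" and lists:
- the central reader's status over time;
- QTcF, with thresholds and absolute change;
- ECG heart rate, as a value and in three classes (below 40, 40 to 120, above 120 bpm);
- relative change in heart rate, in two classes.

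PR, QRS, uncorrected QT and QTcB are not in the list. For the last item, section 4.5.6.4 says "Relative change in HR from baseline will be classified as" either ≤25% or >25%. Section 4.5.1 defines relative change as a signed percentage. Sections 4.6.1 to 4.6.6, on departures from the protocol's statistical section, have no entry on ECG or vital signs.

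**The concern.** Safety is half of the stated objective, and the protocol specifies which cardiac measures are to be summarised and how. The SAP drops several of them silently, so someone comparing the report with the protocol would find protocol-required summaries missing and no reason given. PR and QRS are the conduction intervals. Without them by arm, a modest dose-related lengthening that no reader or investigator calls clinically significant would go unreported. Heart rate at V4, the only scheduled visit after treatment ends, would also go unsummarised. The change class would report large individual falls in the same cell as no change.

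**Working it through.** No power or alpha figure is involved, so the check is a side-by-side comparison followed by arithmetic on the change class.

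**1. Measures required and measures kept**

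| Protocol 9.7.3 | SAP 5.3.3.4 / 5.3.3.5 |
|---|---|
| ECG heart rate, value and change | Value by visit and arm, with a graph; change only as two classes |
| PR, value and change | Absent |
| QRS, value and change | Absent |
| QT, value and change | Absent (QTcF analysed) |
| QTcB, value and change | Absent (replaced by QTcF) |
| Supine heart rate, value and change | Baseline only (5.1.9) |

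Of the five ECG measures named, one is kept under its own name. For QT and QTcB, repolarisation is still covered through QTcF. For PR and QRS nothing replaces them.

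**2. Visits with a heart-rate summary by arm**

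The post-baseline visits are V1, V2, V3 and V4. ECG heart rate exists at V1 and V3. Vital-sign heart rate exists at all four but is not summarised after baseline. So V2 and V4, two of four, have none.

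**3. The relative-change class**

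Formula (SAP 4.5.1): 100 × (value − baseline) / baseline. The pairs below are illustrative assumptions, not trial data.

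| Baseline → visit (bpm) | Relative change | Change class | Rate class |
|---|---|---|---|
| 80 → 50 | (50−80)/80 = −37.5% | ≤25% | 40–120 |
| 80 → 41 | (41−80)/80 = −48.75% | ≤25% | 40–120 |
| 70 → 50 | (50−70)/70 = −28.6% | ≤25% | 40–120 |
| 60 → 39 | (39−60)/60 = −35.0% | ≤25% | <40 |
| 80 → 100 | (100−80)/80 = +25.0% | ≤25% | 40–120 |
| 80 → 101 | (101−80)/80 = +26.25% | >25% | 40–120 |

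Every fall is a negative number and so meets ≤25%; only a rise can reach >25%. The below-40 class picks up one of the four falls. A fall of more than 25% that stays at or above 40 bpm needs 0.75 × baseline > 40, that is a baseline above 40/0.75 = 53.3 bpm. Protocol Appendix B gives a normal range of 50 to 100 bpm, so this covers most of that range. A patient who falls to 40–49 bpm is below that normal range, yet sits in the middle rate class and in ≤25%.

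**The case against.** Five points can be made on the other side.

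- **Rate is still shown.** A reader might infer from the omissions that rate changes by arm cannot be seen at all. The documents do not support that. SAP 5.3.3.5 describes ECG heart rate by arm at ECG visits, overall and by gender, plots its mean with a 95% interval, and counts patients below 40 and above 120 bpm. A mean fall at week 4 or week 24 would be visible. This stands and limits the point.
- **Conduction is partly covered.** A reader might likewise infer that conduction changes are wholly hidden. Clinically significant ones can appear in the reader's shift table by arm, in the listing of clinically significant abnormal ECGs, and as adverse events (protocol 9.7.3). The DSMB receives PR by coded arm (protocol 6.4.3). This stands for clinically significant findings. It does not cover smaller shifts, QRS is not on the DSMB list, and SAP section 2 puts DSMB analyses outside this plan.
- **Fridericia is not new.** Protocol 6.4.3 already names both corrections, and the QTcF analysis is thorough. So the QT and QTcB gap is mainly one of declaration.
- **The class may only be badly worded.** SAP 4.5.6.4 gives no direction, and absolute size may have been meant. The only definition of relative change in the SAP is signed, however. Taking absolute size would count falls but mix them with rises. For weight, SAP 5.3.3.4 does separate decreases from increases.
- **No signal is reported.** Earlier human studies showed no clinically significant ECG change (protocol 1.4.4). That lowers the urgency, but repeated dosing there lasted at most 4 weeks, against 24 here.

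The protocol also lets a SAP clarification prevail (9.7.4). Leaving out a required summary without comment is hard to call a clarification.

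**Conclusion.** The point holds in a limited form. The SAP departs from protocol 9.7.3 without saying so, and four things are lost:
1. any by-arm summary of PR and QRS, which matters for shifts below clinical significance;
2. heart rate at V2 and V4;
3. continuous change from baseline in heart rate;
4. a count of patients with large falls that stay at or above 40 bpm.

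Severity is minor to moderate. Nothing here touches the primary efficacy conclusion.

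The conclusion rests on these assumptions:
- The SAP cites protocol version 5.1, and the version reviewed is 5.0. I assume that section 9.7.3 did not change.
- The table shells are in a separate file that was not available (SAP sections 6 and 7). They may contain further output, but the SAP text does not call for it.
- PR and QRS are in the database, as protocol 9.7.3 says they are collected.
- The signed definition in SAP 4.5.1 applies to heart rate.

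**What to change.** - **SAP 5.3.3.5:** add PR, QRS and QT, as value and absolute change by visit and arm, and add absolute change in heart rate.
- **SAP 5.3.3.4:** add vital-sign heart rate, value and change from baseline, at every visit.
- **SAP 4.5.6.4 and 5.3.3.5:** split relative heart-rate change into decrease of more than 25%, within ±25%, and increase of more than 25%. This also settles the question of direction.
- **SAP 4.6:** record the change from QTcB to QTcF, and declare and justify any other protocol measure that is still left out.

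The cost is SAP wording and a few rows in existing tables. No new data, visits or tests are needed. It should be done before unblinding, so that the summaries are plainly pre-specified.

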## 5.4 Quality of Life

The endpoints will be the 10 sub-scores of the SF-36 and the global score of FFS (see sections 4.5.5.1 and 4.5.5.2).

### **Main analysis**

The population of analysis will be the FAS as described in section 4.3.3. Only the observed cases under treatment will be analysed (see section 4.1.6.3).

#### - Descriptive analysis

Each score/sub-score will be described over time (Baseline and Week 24) using descriptive statistics by treatment group, in terms of:

- Raw values
- Absolute change from baseline

One graph will also be provided describing the raw values (with 95%CI) by treatment group over time.

## 5.5 Exploratory data

### 5.5.1 *Liver biopsy*

The following variables will be described by treatment and by diabetic status, for the biopsies at week 24:

- CRN-S score (S0, S1, S2, S3)
- CRN-S (quantitative)
- CRN-I score (Grades 0, 1, 2)
- CRN-I (quantitative)
- CRN-B score (Grades 0, 1, 2)
- CRN-B (quantitative)
- CRN NAS score (from 0 to 8)
- CRN NAS score (quantitative)
- SAF-I score (Grades 0, 1, 2)
- SAF-I (quantitative)
- SAF-A score (A2, A3, A4)
- SAF-A score (A2-A3, A4)
- SAF-A (quantitative)
- CRN-F score (F0, F1, F2, F3)
- CRN-F score (F0-F1, F2-F3)
- CRN-F score (quantitative)
- Fibrosis Stage (modified Ishak) (Stages 0, 1, 2, 3, 4, 5, 6)
- Fibrosis Stage (modified Ishak) (quantitative)
- Biopsy length (mm)
- Biopsy length ( $\leq 8$ ,  $>8$  mm)
- Iron overload intensity (Absent, mild, moderate, severe)
- Iron overload location (None, Macrophages, Hepatocytes, Both)

All other information collected in the biopsy form will be listed individually in Listings 16.2.

### 5.5.2 *Fibroscan*

The following variables will be described by treatment:

- TE / Stiffness (kPa)
- CAP (dB.m^-1)
- Probe used (M, XL)
- Probe used at Screening and Visit 3 (M-M, M-XL, XL-M, XL-XL)

If the same probes were used (ie M-M or XL-XL):

- Absolute change in TE / Stiffness (kPa)
- Absolute change in CAP (dB.m^-1)

All other information regarding the Fibroscan will be listed individually in Listings 16.2.

### 5.5.3 *Alcohol consumption*

The following parameters will be summarized in a table using descriptive statistics by treatment group at each study visit in the safety set of patients for males and then females:

- Alcohol consumption since last visit (Yes, No)
  - o If consumption, drinks/day (quali)
- Drinks/day (quali) (this value will be defined as 0 for patient with no alcohol consumption)

### 5.5.4 *Immunohistochemistry (semi-quantitative score of ballooning and stellate cell activation)*

If deemed necessary at the time of the availability of the study results, complementary immunohistochemistry analyses could be performed within the year after the end of the study, and specific analyses analysis considered relevant in the scope of the study to understand the safety and efficacy of lanifibranor in patients with NASH could be performed. A separate dedicated SAP will cover this endpoint.

### 5.5.5 *Pharmacokinetic data*

The following variables will be summarized in a table using descriptive statistics by lanifibranor group at each study visit (Visit 1 and Visit 3) in the safety set of patients, overall, by gender (Male, Female), by BMI at baseline (Obese, Non-obese) and by age in class (<65, ≥65 years old):

- Trough values for lanifibranor and its 3 metabolites
- Metabolites ratio defined as the value of the metabolite/value of parent (Lanifibranor) for the 3 metabolites. If the value of parent is 0 or BLQ, then the ratio will be missing.

Four box plots for lanifibranor and its 3 metabolites displaying the trough values will be edited for each lanifibranor group overall.

Some values may be aberrant. In this purpose, only values collected before the treatment intake will be considered in the analyses. BLQ (Below Limit of Quantification) values will be considered as 0.

**6 Tables, Listings and Graphs (TLG)**

See appended document:

INVENTIVA\_NATIVE\_SAP\_Mock\_Up\_TFLs\_Version1.0\_20200513.pdf

**7 Template of tables, listings and graphs**

See appended document:

INVENTIVA\_NATIVE\_SAP\_Mock\_Up\_TFLs\_Version1.0\_20200513.pdf

**8 Appendix 1 - Correspondence between patient number and country**

Country number: first two digits of patient number	Country
00	Belgium
01	Italy
02	France
03	UK
04	Switzerland
05	Spain
06	Portugal
07	Poland
08	Germany
09	Czech Republic
10	Austria
11	Netherlands
12	Australia
13	Canada
14	Mauritius
15	Bulgaria
16	United States
17	Slovenia

## **9 Appendix 2 - Contents of statistical deliverables**

See appended document: INVENTIVA\_NATIVE\_SAP\_Mock\_Up\_TFLs

## **10 Appendix 3 – Strategy for analysis QC**

See appended document: INVENTIVA\_NATIVE\_SAP\_Mock\_Up\_TFLs

